#### **Pooling Across Institutions**

Analyses will be performed using data pooled across institutions. Analyses to justify pooling will include the following:

- The primary endpoint presented by institution.
- An assessment of the 'poolability' of the institutions using a 2-by-(number of institutions) contingency table of outcome versus institution. Fisher's Exact Test will be used to assess homogeneity. Institutions with fewer than five subjects will be combined based on geographic region if possible.
- If the institutions are found to be significantly heterogeneous with respect to the

primary endpoint, additional analyses will be conducted to assess differences between institutions in baseline and procedural variables that might explain differences in primary outcome.

#### **Other Analysis Methods**

Kaplan-Meier plots of time-to-event variables will be constructed for clinical outcomes.

#### 21.Data management

#### **Data collection and processing**

Subject data will be collected in a secure electronic data capture (EDC) system via the Internet. The Principal Investigator or Sub-investigator must ensure the accuracy and completeness of the recorded data entered into the EDC and also by providing his/her electronic signature on the appropriate paper Case Report Forms (CRF). The Investigator's signature for specific CRF will be documented in compliance with local regulations.

Changes to data previously submitted to the sponsor will require a new signature by the Investigator to acknowledge and approve the changes. The coordinating or primary study site team will compare the data entered into EDC and paper CRF for discrepancy and require a response from the site PI/Sub-I.

Audits may be performed for quality assurance of data handling against source documents

Visual and/or computer data review will be performed to identify possible data discrepancies. Manual and/or automatic queries will be created in the EDC system and will be issued to the site for appropriate response. The trial center will be responsible for resolving all queries in the database in a timely manner.

#### 22.Monitoring

Monitoring of trial centers will be made periodically during the trial, as outlined in the trial monitoring plan, to ensure that all aspects of the current, approved protocol/amendment(s) are followed.

Original source documents will be reviewed for verification of data in the electronic database. The Investigator/institution guarantees direct access to original source documents, including electronic medical records, if applicable, by monitoring personnel, their designees, and appropriate regulatory authorities. In the event that the original medical records cannot be obtained for a subject that is seen by a non-trial physician at a non-trial institution, photocopies of the original source documents must be made available for review. In the event such records cannot be released, the study site will allow verification of the source data by passive viewing of the source electronic

medical record screen handled exclusively by the site coordinator/investigator(s).

The trial also may be audited for quality assurance by monitors or its designees, as well as inspected by appropriate regulatory authorities.

It is important that the Investigator and relevant trial personnel are available during monitoring visits, audits and inspections, and that sufficient time is devoted to the process.

#### **Monitoring plan**

Designated monitor(s) funded and supported by the PI will undertake site monitoring. Such monitoring visits will be conducted for. sites on a six monthly basis

## **23.Adverse Events**

All Adverse Events (AE) and Serious Adverse Events (SAE) will be reported through EDC and analyzed through study follow-up period.

Term	Definition
Adverse Event (AE)	Any untoward medical occurrence in a subject. This definition does not imply that there is a relationship between the adverse event and the treatment under investigation.
	Note 1: In addition, the definition of AE applies to any event with an onset post- randomization procedure or to any underlying diseases, present at baseline, that exacerbate in severity post- randomization procedure. Therefore, any underlying disease that was present at the time of enrollment is not to be reported as an AE, but any increase in the severity in the underlying disease is to be reported as an AE. This definition includes events occurring in the follow-up period.
Serious Adverse Event (SAE)	
 
An adverse event that:
 
led to death;
 
led to a serious deterioration in the health of the subject that: 
 
resulted in a life-threatening illness or injury,
 
resulted in a permanent impairment of a body structure or a body function,
 
 
 

Clinical events to be considered and reported as expected SAE include, but are not limited to:

- MAE (see definitions)
- Stent Thrombosis
- Bleeding complication as per GUSTO definition
- Vascular event requiring target limb surgical or endovascular intervention or amputation
- Any hospitalization

#### Relationship

The Investigator must assess the relationship of the adverse event to the participation in the study and use of antiplatelet drugs using the following criteria categories and definitions:

- Unrelated: The adverse event is determined to be due to a concurrent illness or effect of another device/drug and is not related to the study related drugs
- Possible: The adverse event is determined to be potentially related to the study related drugs, and an alternative etiology is equally or less likely compared to the potential relationship to the study related drug
- Probable: There is a strong relationship to study related drug or recurs on rechallenge, and another etiology is unlikely
- Highly Probable: There is no other reasonable medical explanation for the event

The Investigator must assess the relationship of the adverse event to the study related drug using the following categories and definitions:

- Unrelated The adverse event is determined to be due to a concurrent illness or effect of a device/drug and is not related to the study related drug use
- Possible The adverse event is determined to be potentially related to the index procedure, and an alternative etiology is equally or less likely compared to the potential relationship to study related drug use
- Probably There is a strong relationship to index procedure, or recurs on rechallenge, and another etiology is unlikely
- Highly Probable There is no other reasonable medical explanation for the event

#### Outcome

The Investigator must document the outcome of the AE using the following categories:

- Resolved without residual effects
- Resolved with residual effects
- Recovering/Resolving
- Not Recovered/Not Resolved
- Death
- Unknown

#### **Reporting Requirements**

Trial personnel must report to the study PI's office any SAE or MAE by fax within 24 hours of learning of the event. When faxing in notification of an event, a fax confirmation report must be retained at the site as adequate documentation of timely event reporting. Source documentation should record when the site became aware of the event. Trial personnel must forward follow-up information and the completed adverse event CRF to the as the event continues and/or resolves.

All adverse events will be recorded in the electronic database managed by the primary study team at the primary institution and report them at each DSMB meeting. A description of the event, including the start date, resolution date, action taken, assessment, and outcome should be provided, along with the Investigator's assessment of the relationship between the AE and the trial treatment. All adverse events also need to be reported to the local IRB within 24 hours of knowledge of the study team.

#### 24. Risk-benefit analysis

Based on review of the scientific literature, outcomes of design verification, the results of preclinical studies, and known adverse drug effects, the benefit of treatment with the aspirin and clopidogrel post-iliac, FP and BTK endovascular intervention outweighs the risks. However, the effect of unknown factors accounting for unanticipated side effects cannot be completely excluded, therefore observation and follow-up of subjects is required as outlined in the protocol.

Risks associated with aspirin and clopidogrel drug therapy may include:

- a. Allergic reaction
- b. Amputation
- c. Aneurysm
- d. Angina/coronary ischemia
- e. Arrhythmia
- f. Arteriovenous fistula
- g. Death

- h. Drug-drug interactions
- i. GI bleeding
- j. Hemorrhage/hematoma
- k. Hypotension/Hypertension
- l. Myocardial infarction (MI)
- m. Need for urgent intervention or surgery
- n. Pseudoaneurysm
- o. Renal insufficiency or failure
- p. Restenosis of stented artery
- q. Rupture of the retroperitoneum or other organ
- r. Stroke
- s. Thrombosis / Thrombus
- t. Tissue ischemia/necrosis
- u. Vasospasm
- v. Vessel injury, examples include perforation, dissection, intimal tear, rupture
- w. Vessel occlusion

#### **Risk minimization**

The risks associated with the aspirin and clopidogrel use are relatively well established, and the preceding risks represent the most up-to-date understanding of risks associated. The study team will employ measures throughout the course of this investigation, to minimize these risks to subjects choosing to participate. In general, efforts will be made to minimize these risks by:

- i. Selecting Investigators who are experienced and skilled clinicians and expert in endovascular procedures
- ii. Clearly defining inclusion/exclusion criteria to ensure only appropriate subjects are enrolled
- iii. Ensuring that the treatment and follow-up of the subjects are consistent with current medical practices

Specifically, every subject participating in this trial will undergo the following:

- a. Medical history, physical examination, and laboratory assessment prior to the procedure to identify factors which may increase risk
- b. Required review of anti-coagulant and anti-platelet medication before and after enrolment into the trial

## Data safety monitoring board (DSMB)

A DSMB will meet every 6 months as scheduled or sooner based on reported AE and review all adverse events at these meetings and make recommendations to the study executive committee regarding the conduct and continuation of the trial, with/without recommendations for the study team(s) and or the executive committee/PI. The DSMB will include 5 members with a chair and all decisions will be adopted by a clear majority and all proceeding minutes recorded and stored with the primary study team/PI's office. A minimum of 3 members will be required to conduct the proceedings of the DSMB.

## **Clinical events committee (CEC)**

A Clinical Events Committee with pertinent expertise that reviews and adjudicates important endpoints and relevant adverse events reported by trial Investigators.

Committee membership will include practitioners of peripheral endovascular procedures, as well as other experts with the necessary therapeutic and subject matter expertise, to adjudicate the event categories outlined above. CEC responsibilities, qualifications, membership, and committee procedures are outlined in the CEC charter.

The CEC will adjudicate the following events:

- All Deaths
- Myocardial infarction (MI) that occurs during index hospitalization
- Target lesion revascularization (TLR), surgical or endovascular
- Target vessel revascularization (TVR), surgical or endovascular
- Target limb/extremity revascularization (TER), surgical or endovascular
- Amputation of index limb or any amputation
- Stent Thrombosis or target iliac, FP or BTK vessel occlusion
- Any urgent limb/extremity revascularization surgical or endovascular procedure
- Bleeding events
- Any stroke

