## Protocol Synopsis

## ASPiRE Antiplatelet Strategy for Peripheral Arterial Interventions for Revascularization of Lower Extremities

PI	Name: [name]
	[contact]
	Email: [contact]
TRIAL OBJECTIVE	
Primary Objective	To evaluate whether clopidogrel 75 mg daily on a background of aspirin 81 mg/d for U.S. sites (75-100 mg/d for international sites) for clinically indicated duration or an additional 12 months will lead to an increased rate of primary patency, limb salvage, non-fatal myocardial infarction (MI), ischemic stroke, and survival, in patients receiving endovascular treatment of PAD at end of study treatment
Control Arm	clopidogrel 75 mg daily on a background of aspirin 81 mg/d for U.S. sites (75-100 mg/d for international sites) for clinically indicated duration with a minimum of 30 days.
Test Arm (as applicable)	clopidogrel 75 mg daily on a background of aspirin 81 mg/d for U.S. sites (75-100 mg/d for international sites) for clinically indicated duration + 12 months
Endovascular	Iliac
interventions included	Femoropoliteal
	Below-the knee
TRIAL DESIGN	
Trial Design	Prospective, two-arm, multicenter randomized clinical trial.
PlannedNumber of Subjects	202 subjects will be enrolled in each arm (total subjects = 404)
Clinically indicated dual	Clinically indicated DAPT duration will be based on the longest pre-
antiplatelet therapy	discharge following an index peripheral intervention procedure,
(DAPT) duration	DAPT duration. This will be determined based on: peripheral
	intervention device IFUs, preceding coronary intervention, acute
	coronary syndrome or other guideline-based clinical or device

	specific DAPT durations.
PlannedNumber of Sites / Countries	Approximately 18 investigational centers in the U.S are expected to participate.
	No center will be allowed to enroll more than 40% of planned total enrollment.
Primary Endpoint	Primary Endpoint (subject-based): The first occurrence of index limb arterial occlusion, surgical intervention, endovascular intervention, amputation of the affected limb (vessel occlusion or failure), MI, ischemic stroke or death at 12 months from index procedure or end of study treatment, whichever is longer
Secondary Endpoints	Secondary Endpoints through end of study treatment:
	• The first occurrence of any individual component of the primary endpoint

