	• First occurrence of the following during follow-up: cardiovascular death, or MI, or ischemic stroke, or any amputation above the ankle.
	• Severe bleeding defined according to the Global Utilization of Streptokinase and Tissue plasminogen activator for Occluded coronary arteries (GUSTO) classification
Tertiary Endpoints	• Moderate bleeding defined according to the Global Utilization of Streptokinase and Tissue plasminogen activator for Occluded coronary arteries (GUSTO) classification
Randomization	
 
Patients scheduled for a planned discharge will be randomized on a 1:1 basis using a computerized central randomization portal available through RedCap® to either of the following treatment groups:         
 
ASA (81 mg U.S. sites; 75-100 mg international sites) + clopidogrel: for clinically indicated duration (control arm)
 
ASA (81 mg U.S. sites; 75-100 mg international sites) + Clopidogrel 75mg: for clinically indicated duration +12m (treatment arm)
 
 
 
Randomization will be performed at the within 2 weeks of an eligible procedure
 

Follow-up schedule	All potential subjects will be evaluated for enrollment after the index procedure pre-discharge or within 14 days of the procedure. Follow- up schedule will include patient visits at 30 days and q6 months till the end of study treatment The trial will be considered complete with regard to the primary endpoint after all enrolled subjects have

	completed a 12-month or end of study treatment follow-up evaluation, have died, have a documented premature discontinuation, or whose follow-up window has closed. Follow-up window is $\pm 7$ days for the 30-day visit and $\pm 15$ days for all other visits.

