## 6. Trial endpoints

Clinical endpoints will be analyzed in all subjects who are enrolled, regardless of whether the trial treatment administered successfully completed for the desired duration. A subject will be considered enrolled in the trial when he/she is randomized to one of the treatment arms of the study. All endpoints are subject-based unless otherwise specified.

The primary endpoint is subject-based of the longer of a 12-month or end of study treatment endpoint of the first occurrence of index limb arterial occlusion, surgical intervention,

endovascular intervention, amputation of the affected limb (primary patency and limb salvage), MI, ischemic stroke or death (survival)

The secondary endpoints are subject-based on the longer of a 12-month or end of study treatment endpoints that include: (a) the first occurrence of any individual component of the primary endpoint, (b) the first occurrence of the following during follow-up: cardiovascular death, or MI, or ischemic stroke, or any amputation above the ankle and (c) severe bleeding defined according to the Global Utilization of Streptokinase and Tissue plasminogen activator for Occluded coronary arteries (GUSTO) classification

The tertiary endpoint is based on the longer of a12-month or end of study treatment moderate bleeding according to the GUSTO classification

Clinically indicated DAPT duration will be based on the longest pre-discharge following index peripheral intervention procedure DAPT duration. This will be determined based on: peripheral intervention device IFUs, preceding coronary intervention, acute coronary syndrome or other guideline-based clinical or device specific DAPT duration.

Study treatment will be discontinued at the first occurrence of a primary endpoint as defined in the table below. Patients, however, can resume taking aspirin, Clopidogrel, or both based on their provider's clinical decision.

Primary endpoint definition(s)	Secondary/Tertiary endpoint definition(s)
Occlusion of the target limb documented by any imaging procedure performed clinically	As described in section 6, except for:
any maging procedure performed ennearly	GUSTO bleeding criteria:
Any surgical or endovascular	1. Severe or Life-threatening: Intracerebral hemorrhage resulting in substantial
revascularization procedure on the index limb	hemodynamic compromise requiring treatment
Amputation above the ankle of the index	2. Moderate: Requiring blood transfusion but not resulting in hemodynamic

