limb Death from any cause	compromise
Ischemic stroke: An episode of neurological dysfunction caused by focal cerebral, spinal, or retinal infarction confirmed by a neurologist	3. Mild: Bleeding that does not meet above criteria
MI: Detection of a rise in cardiac troponin	
(cTn) with at least one value 3x above the	
99th percentile upper reference limit (URL) and with at least 1 of the following:	
Symptoms of ischemia	
• New or presumed new significant ( $\geq 1$	
mm) ST- segment–T wave (ST–T)	
changes or new left bundle branch block (LBBB)	

• Development of pathological Q waves in the ECG	
--	--

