## 9. Method of assigning subjects to treatment

Patients scheduled for a planned discharge will be randomized on a 1: 1 basis using a central computerized randomization portal available through RedCap® to either of the following treatment groups:

ASA (81 mg/d for U.S. sites; 75-100 mg for international sites) + clopidogrel:for clinically indicated duration with a minimum of 30 days (control arm)

ASA (81 mg/d for U.S. sites; 75-100 mg for international sites) + clopidogrel 75 mg: for clinically indicated duration + 12m (treatment arm)

An inclusion and exclusion checklist needs to be completed via computerized randomization portal available through  $RedCap^{(R)}$  prior to randomization of the subject.

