## **10.** Trial population

Table 1 on the following pages outlines the specific inclusion and exclusion criteria for the trial, according to general and angiographic categories. Before enrollment in the trial, a subject must meet all of the inclusion and none of the exclusion criteria.

Key Inclusion Criteria	General:
	
 
Signed informed consent
 
At least 18 years old
 
Documented symptomatic iliac, femoropopliteal (FP) or below-the knee artery (BTK) atherosclerotic disease (Rutherford/Becker category 2, 3 or ≥4)
 
Undergone clinically indicated uncomplicated endovascular intervention to one or more locations of the iliac, femoropopliteal below-the knee arteries
 
Estimated survival ≥1 year in the judgment of the primary operator
 
Pre-index procedure use of ASA, clopidogrel or both at any dose
 

	
 
De novo or restenotic lesions in the
 

	• De novo or restenotic lesions in the

	
 
common and/or external iliac artery, superficial femoral artery (SFA), popliteal artery, tibio-peroneal (TP) trunk, anterior tibial (AT) artery, peroneal artery (PA) or posterior tibial (PT) artery (applies to all target lesions if multiple)
 
Subjects with multiple planned procedures can be enrolled after the completion of the last planned procedure.
 

Key Exclusion Criteria	General:
	• Complicated qualifying procedure (perforation, flow limiting dissection, distal embolization requiring re- intervention, need for repeat endovascular, surgical revascularization, amputation or blood transfusion prior to hospital discharge following an index procedure
	• Extended hospital stay >7 days following the index procedure
	• Allergy to aspirin or clopidogrel
	• Life expectancy less than 12 months due to other medical co-morbid condition(s) that could limit the subject's ability to participate in the trial, limit the subject's compliance with the follow-up requirements, or impact the scientific integrity of the trial
	• Known hypersensitivity or contraindication to contrast dye that, in the opinion of the investigator, cannot be adequately pre-medicated.
	• Intolerance to antiplatelet, anticoagulant, or thrombolytic medications
	• Platelet count <90,000 mm  or >600,000 mm 
	• Serum creatinine >2.5 mg/dL
	
 
Dialysis-dependent end stage renal disease
 

• Pregnancy	

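### The Clinical Events Committee list limits MI, alone among its ten events, to the index hospital stay, although MI is an endpoint for the whole of follow-up

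*Combined protocol and SAP*

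**What the plan says.** Section 24, under the Clinical events committee heading, gives ten bullets that the CEC will adjudicate. The MI bullet reads "Myocardial infarction (MI) that occurs during index hospitalization". Deaths, strokes, amputations and bleeding are listed without a time limit. The revascularisation and vessel-occlusion bullets are restricted by site or urgency, but not by time.

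MI enters the endpoints three times:

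- The synopsis defines the primary composite to include "MI, ischemic stroke or death at 12 months from index procedure or end of study treatment, whichever is longer", and Section 6 uses the same period.
- Secondary endpoint (a) in Section 6 is "the first occurrence of any individual component of the primary endpoint", so MI is an endpoint in its own right.
- Secondary endpoint (b) is "the first occurrence of the following during follow-up: cardiovascular death, or MI, or ischemic stroke, or any amputation above the ankle".

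The definition table in Section 6 begins "MI: Detection of a rise in cardiac troponin" and requires symptoms or ECG change as well. It sets no time limit.

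On timing, the synopsis states "All potential subjects will be evaluated for enrollment after the index procedure pre-discharge or within 14 days of the procedure", and Section 9 states "Patients scheduled for a planned discharge will be randomized on a 1: 1 basis". Section 10 makes "Extended hospital stay >7 days following the index procedure" an exclusion.

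The CEC's general remit is wider than its list. Section 24 has it adjudicate important endpoints, and Section 15 has it review clinical events arising in the trial. Section 24 leaves responsibilities and procedures to a CEC charter. The Appendix gives clinical adjudication to an independent data oversight and safety monitoring board instead.

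**The concern.** An adjudication list should cover each endpoint component for as long as that component counts. For MI it stops at the index stay, and the endpoint continues for at least a year. What drops off the list is later non-fatal MI; a later fatal MI is reached through the deaths bullet.

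This matters because classifying an MI takes judgement: a troponin threshold must be met together with symptoms or ECG findings. The trial describes no placebo and no masking of sites, and footnote 5 to Table 2 in Section 12, on refills for the longer arm, shows that sites know the allocation. Independent adjudication is the usual protection in that setting. If the list is followed as written, later non-fatal MI would not receive the CEC adjudication listed for the other event types. The endpoints in which MI carries most weight, namely MI alone and the cardiovascular composite, are the more exposed.

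**Working it through.** No figure in the plan bears on this point, and the sample size does not depend on it. The check is a count and a comparison of time windows.

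**Step 1: the CEC list (Section 24).** The bullets are deaths; MI; target lesion revascularisation; target vessel revascularisation; target limb revascularisation; amputation; stent thrombosis or target vessel occlusion; urgent limb revascularisation; bleeding; stroke. That is 10 items. Items with a time limit: 1 (MI). Items without: 10 − 1 = 9.

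**Step 2: endpoint components against the list, on time limits only.**

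| Endpoint | Components | Listed without a time limit |
|---|---|---|
| Primary (synopsis, Section 6) | occlusion, surgical intervention, endovascular intervention, amputation, MI, ischemic stroke, death = 7 | 7 − 1 = 6 |
| Cardiovascular composite (Section 6) | cardiovascular death, MI, ischemic stroke, amputation above the ankle = 4 | 4 − 1 = 3 |
| MI as an individual component (Section 6) | MI = 1 | 1 − 1 = 0 |

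The contrast concerns time only. The occlusion bullet names the target vessel, whereas the endpoint is occlusion of the index limb, so that bullet may be narrower in another respect.

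**Step 3: where the listed MI window falls.**

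- Randomised at discharge, or after it within the 14 days: the index stay is over, so the listed window lies wholly before randomisation.
- Randomised earlier in the stay: only the remaining inpatient days come after randomisation. A stay of more than 7 days is an exclusion, so these are few unless discharge is delayed after randomisation.

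**Step 4: the window against the treatment contrast.** The arms share a regimen for the clinically indicated duration, with a control-arm minimum of 30 days (synopsis, Section 9). They are assigned to differ only after that. Since 7 < 30, an index stay within the entry limit ends while both arms are assigned the same treatment. MIs in the period when assigned treatment differs are all off the list, apart from fatal ones.

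**Step 5: is later MI at least captured?** Yes. Section 23 treats major adverse events as reportable serious events and requires notice to the study office within 24 hours, and Section 25 names MI among the major adverse events. The gap is in listed adjudication, not in reporting.

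**The case against.** The strongest reply is that the general remit already covers later MI. A component of the primary endpoint is plainly an important endpoint, Section 15 sets no time limit, the list does not say that it is exhaustive, and the charter may be wider. This stands to the extent that it rules out one reading: a reader might infer that later MIs will go unadjudicated, and the documents do not establish that. It does not remove the inconsistency. A time limit placed on one event out of ten invites the committee to apply it, and no passage expressly extends the item.

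A reader might also infer that a later non-fatal MI would stand on the site's classification with no review at all. That goes too far. The Data Safety Monitoring Board reviews all adverse events (Section 24), and the Appendix assigns clinical adjudication to an independent board. Safety review is not endpoint adjudication, however, and the Appendix adds uncertainty about who adjudicates.

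It is tempting to cite the Institutional Review Board paragraph in Section 25, which names MI without a time limit, as a further contradiction. It is not one: it sets a notification duty, which can coexist with a narrower adjudication list.

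Finally, Section 15 names centre and subject identity, but not treatment arm, as masked from the CEC. That is a separate matter which the charter may settle, and this point does not rest on it.

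**Conclusion.** The inconsistency is real and clear on the text. MI is the 1 time-limited item of 10, it belongs to three endpoints that run to the later of 12 months and the end of study treatment, and its listed window lies largely or wholly before randomisation.

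The consequence is conditional. If the list is followed, later non-fatal MI would not receive listed CEC adjudication in a trial that describes no masking of sites. Whether the list would be followed depends on how the general remit is read and on a charter that was not available.

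A reader might go on to infer a biased primary result. The documents do not support that. They give no MI rate and no split of the expected events by component, so neither the number of MIs affected nor any effect on a treatment comparison can be calculated. Expressing the index stay as a share of follow-up time would not help, since a share of calendar time is not a share of MIs.

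The wording should be corrected because the listed rule does not match the endpoint and the change is simple.

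**What to change.** Change the MI item in Section 24 to cover any myocardial infarction through the end of the primary endpoint period, starting from the same point as the primary endpoint and adjudicated against the Section 6 definition. Align the CEC charter with it. Reconcile the Appendix statement on who performs clinical adjudication with Section 15 and with the CEC and Data Safety Monitoring Board paragraphs of Section 24.

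The cost is a wording change to the protocol and charter, more MI events for an existing committee, and collection of troponin and ECG source records for them. The number of extra events cannot be given without an MI rate. Later MIs are already reportable, so no new event report is needed, but assembling the records is extra site work. Section 22 recognises that records from outside institutions may not always be released, so some cases may have to be judged on incomplete evidence. Sample size and treatment are unaffected.
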